## **6.2 Study Assessments/Procedures: Randomization to Hospital Discharge (Daily)**

- Study Variable Data Collection
  - Medication Assessment
  - Assess for clinical diagnosis of deep vein thrombosis (DVT) or pulmonary embolism (PE)
  - Oxygen/Ventilation assessment including S/F ratio, ventilation type, & vasopressor use (if applicable)
  - ARDS Assessment by Berlin Diagnostic Criteria (if applicable)
  - ICU admission/discharge information (if applicable)
  - Death date (if applicable)
  - Safety Outcomes: Dehydration, Seizure, Atrial or ventricular arrhythmia, Cardiac arrest, Symptomatic Hypotension, Acute kidney injury, Receipt of renal replacement therapy, Symptomatic hypoglycemia
  - Hospital discharge including patient destination at discharge

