## 11.2 Safety Monitoring

Assuring patient safety is an essential component of this protocol. Each participating investigator has primary responsibility for the safety of the individual participants under his or her care. The Investigators will determine daily if any adverse events occur during the period from enrollment through **study day 7** or hospital discharge, whichever occurs first and will determine if such adverse events are reportable. Thereafter, adverse events are not required to be reported unless the investigator feels the adverse event was related to study drug or study procedures.

The following adverse events will be considered reportable and thus collected in the adverse event case report forms:

- Serious adverse events
- Non-serious adverse events that are considered by the investigator to be related to study procedures or of uncertain relationship (Appendix C)
- Events leading to permanent discontinuation of study drug

Study-specific clinical outcomes (Primary, Secondary and Safety Outcomes and Assessments During the Study), including serious outcomes such as organ failures and death, are systematically recorded in the case report forms and are exempt from adverse event reporting unless the investigator deems the event to be related to the administration of study drug or the conduct of study procedures (or of uncertain relationship) as outlined in Appendix C.

After randomization, adverse events must be evaluated by the investigator. If the adverse event is judged to be reportable, as outlined above, then the investigator will report to the Clinical Coordinating Center (CCC) their assessment of the potential relatedness of each adverse event to the study drug or protocol procedure via electronic data entry. Investigators will assess if there is a reasonable possibility that the study procedure caused the event, based on the criteria outlined in Appendix C. Investigators will also consider if the event is unexpected. Unexpected adverse events are events not listed in the study protocol and the package insert for the study drugs will also determine if adverse events are unanticipated given the patient's clinical course, previous medical conditions, and concomitant medications.

If a patient's treatment is discontinued as a result of an adverse event, study site personnel must also report the circumstances and data leading to discontinuation of treatment in the adverse event case report forms.

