## 11.3 Serious Adverse Events

Serious adverse event collection begins after randomization and study procedures have been initiated. If a patient experiences a serious adverse event after consent, but prior to randomization or starting study procedures, the event will NOT be collected. Study site personnel must alert the CCC of any **serious and study procedure related** adverse event within 24 hours of investigator awareness of the event. Alerts issued via telephone are to be immediately followed with official notification on the adverse event case report form. See Appendix C for reporting timelines for serious, unexpected, study related events (SAEs) and serious, unexpected suspected adverse reactions (SUSARs)

As per the FDA and NIH definitions, a serious adverse event is any adverse event that results in one of the following outcomes:

- Death
- A life-threatening experience (that is, immediate risk of dying)
- Prolonged inpatient hospitalization or re-hospitalization

As per <http://www.fda.gov/Safety/MedWatch/HowToReport/ucm053087.htm>: Report if admission to the hospital or prolongation of hospitalization was a result of the adverse event. Emergency room visits that do not result in admission to the hospital should be evaluated for one of the other serious outcomes (e.g., life-threatening; required intervention to prevent permanent impairment or damage; other serious medically important event).

- Persistent or significant disability/incapacity

As per <http://www.fda.gov/Safety/MedWatch/HowToReport/ucm053087.htm>: Report if the adverse event resulted in a substantial disruption of a person's ability to conduct normal life functions, i.e., the adverse event resulted in a significant, persistent or permanent change, impairment, damage or disruption in the patient's body function/structure, physical activities and/or quality of life.

Reportable serious adverse events that may not result in death, be life-threatening, or require hospitalization may be considered serious adverse events when, based upon appropriate medical judgment, they may jeopardize the patient and may require medical or surgical intervention to prevent one of the outcomes listed in this definition. Serious adverse events will be collected until hospital discharge, regardless of the investigator's opinion of causation.

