### **C.3. Clinical Outcomes that may be Exempt from Adverse Event Reporting**

Study-specific outcomes of acute respiratory infection, COVID-19, and critical illness will be systematically collected for all patients in both study group and are exempt from adverse event reporting unless the investigator considers the event to be Definitely or Possibly Related (or of an Uncertain Relationship) to the study drug or study procedures. Examples of study-specific clinical outcomes include:

- Death not related to the study procedures
- Neurological events
  - Seizure
- Cardiovascular events
  - Receipt of vasopressors
  - Atrial or ventricular arrhythmia
  - Cardiac arrest
- Respiratory events
  - Hypoxemia requiring supplemental oxygen
  - Acute respiratory distress syndrome
  - Receipt of mechanical ventilation
  - Receipt of extra-corporeal membrane oxygenation
- Gastrointestinal events
  - Elevation of aspartate aminotransferase or alanine aminotransferase
  - Acute pancreatitis
- Renal events
  - Acute kidney injury
  - Receipt of renal replacement therapy
- Endocrine events
  - Symptomatic hypoglycemia
- Hematologic or coagulation events
  - Neutropenia, lymphopenia, anemia, or thrombocytopenia
- Dermatologic events
  - Severe dermatologic reaction (e.g., Steven's Johnson Syndrome)

Note: A study-specific clinical outcome may also qualify as a reportable adverse event. For example, a ventricular arrhythmia that the investigator considers Definitely or Possibly Related to the study drug would be both recorded as a study-specific clinical outcome and reported as a Serious and Definitely or Possibly Related Adverse Event.

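### Four of the 16 outcomes that Appendix C.3 exempts from adverse event reporting have no listed post-baseline collection, and for serious cases graded unrelated the exemption contradicts Section 11.3

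*Combined protocol and SAP*

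**What the plan says.** All references are to the combined protocol and SAP.

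- **Section 11.2, reportable events.** Three classes go on the adverse event forms: serious events (no relatedness condition is attached), non-serious events judged related or of uncertain relationship, and events that lead to permanent discontinuation of study drug.
- **Section 11.2, exemption.** The exempt class is defined as "Study-specific clinical outcomes (Primary, Secondary and Safety Outcomes and Assessments During the Study), including serious outcomes such as organ failures and death". These outcomes "are systematically recorded in the case report forms and are exempt from adverse event reporting unless the investigator deems the event to be related" to study drug or procedures, or of uncertain relationship.
- **Appendix C.3.** Study-specific outcomes "will be systematically collected for all patients in both study group and are exempt from adverse event reporting unless the investigator considers the event" related or of uncertain relationship. Sixteen outcome lines follow, introduced as examples. Among them are "Elevation of aspartate aminotransferase or alanine aminotransferase", "Acute pancreatitis", "Neutropenia, lymphopenia, anemia, or thrombocytopenia" and severe dermatologic reaction.
- **Section 6.2, daily collection after randomization.** "Safety Outcomes: Dehydration, Seizure, Atrial or ventricular arrhythmia, Cardiac arrest, Symptomatic Hypotension, Acute kidney injury, Receipt of renal replacement therapy, Symptomatic hypoglycemia", together with medication, thrombosis, oxygen and ventilation, vasopressor, ARDS, ICU, death and discharge data.
- **Section 11.3.** "Serious adverse events will be collected until hospital discharge, regardless of the" investigator's view of causation.
- **Opening of Appendix C.** The serious events that sites must send to the coordinating center within 24 hours are described as those that are serious and possibly due to study drug or procedure, or of uncertain relatedness.

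**The concern.** Exempting trial outcomes from adverse event reporting is reasonable when the same events are captured elsewhere for every patient, because the arms can then be compared without relying on a causality judgement. That justification has to hold for each exempt event. If an event is on the exempt list but is not collected as an outcome, the exemption removes one route of capture without supplying the other.

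What is at stake is the randomized safety comparison for serious events. Appendix C has the DSMB review reported adverse events and clinical outcomes. A serious pancreatitis or skin reaction that a blinded investigator grades as probably not related would reach neither stream at a site that follows C.3, unless it led to permanent discontinuation of study drug or to death. Section 7.1 plans 15 patients per arm, so one unrecorded event is 1/15 = 6.7% of an arm.

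**Working it through.** The plan states no figure on this point. The check matches each C.3 line to the assessments listed after baseline, and then sets the reporting rules side by side.

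**Step 1. Match the C.3 lines.** Sources: Sections 5.2, 5.3, 6.2, 6.2.1 and 6.3, Appendix A and Appendix E.

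| C.3 outcome | Listed collection after baseline |
|---|---|
| Death | 6.2; Appendix A |
| Seizure | 6.2 |
| Vasopressors | 6.2 |
| Arrhythmia | 6.2 |
| Cardiac arrest | 6.2 |
| Hypoxemia needing oxygen | 6.2 |
| ARDS | 6.2; Appendix A |
| Mechanical ventilation | 6.2 |
| ECMO | Appendix E, only within composite score 9 |
| AST/ALT elevation | none |
| Acute pancreatitis | none |
| Acute kidney injury | 5.3; 6.2 |
| Renal replacement therapy | 5.3; 6.2 |
| Symptomatic hypoglycemia | 6.2 |
| Neutropenia, lymphopenia, anemia, thrombocytopenia | none named |
| Severe dermatologic reaction | none |

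Result: 12 lines matched and 4 unmatched; 4/16 = 25%. Liver function tests are listed only in the baseline data (Section 6.1). SOFA is repeated once, on Day 3 (Section 6.2.1.2). The documents do not give its components, so whether it covers any part of the cytopenia line cannot be settled from them.

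**Step 2. Compare with Section 11.2's definition.** The exempt class there consists of the primary, secondary and safety outcomes and the on-study assessments. By Step 1 the four lines are named in none of these. Section 11.2 read alone therefore does not exempt them, while C.3 lists them as exempt.

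**Step 3. Trace an event graded probably or definitely not related, of one of the four types, that does not lead to permanent discontinuation.**

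| Case | Following C.3 | Following 11.3 and the 11.2 reportable list |
|---|---|---|
| Serious | Exempt; no listed outcome field | Collected until hospital discharge |
| Non-serious | Not reportable | Not reportable |

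The rules diverge only in the first row. In the second row the event is outside Section 11.2's reportable classes whether or not C.3 mentions it.

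**Step 4. Ask whether the text settles the first row.** Section 11.3 and the 11.2 list point to collection. The 11.2 exemption, which follows that list and expressly reaches serious outcomes, points the other way. So does C.3, which restores reporting only for related or uncertain events. The opening of Appendix C also describes reportable serious events by relatedness, although that sentence can be read as governing only the 24-hour notice. No sentence in the text provided says which rule prevails.

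**The case against.** The strongest reply is that nothing serious need be lost. Section 11.2 puts serious adverse events on the forms without a relatedness condition, and Section 11.3 collects them to discharge regardless of causation. Section 11.2's definition already leaves the four items out of the exemption, and the title of C.3 says only that outcomes may be exempt. Events leading to permanent discontinuation are reportable, and deaths are dated. The case report forms are not part of the documents and the C.4 decision tree is not shown; either could resolve the matter. Section 9.1 names none of the four among the risks of either product, and the trial is a single-center study of 30 patients.

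Much of this stands, and it rules out a stronger reading. A reader might infer that serious unrelated cases are recorded nowhere, that every such event is lost whether serious or not, or that the final safety table would show zero by construction. The documents do not support any of these. Loss of a serious case occurs only if a site resolves the conflict in favor of C.3. Non-serious unrelated events are unreportable under Section 11.2 in any case, so C.3 does not cause their absence. Related, uncertain and discontinuation events are reported under either rule.

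The reply does not remove the contradiction. That Section 11.2 leaves the four items out while C.3 names them is itself an inconsistency. The exemption's express reach to serious outcomes means a site could follow C.3 in good faith and omit a case that Section 11.3 requires.

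**Conclusion.** The point holds as an internal inconsistency in safety capture. Four of 16 C.3 lines (25%) are exempted on a premise of systematic collection that no listed post-baseline assessment supports, and they lie outside Section 11.2's own exempt class. For serious cases of these types graded unrelated, C.3 and Section 11.3 give opposite instructions.

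The number of events affected cannot be estimated: the documents give no rates for these events, and the result depends on which rule the site follows. With 30 patients the count is likely to be small, but so is the number of events on which the safety comparison rests.

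The conclusion assumes that the assessment lists in the protocol reflect what the case report forms collect, that the Day 3 SOFA is not a systematic record of the cytopenias, and that the C.4 decision tree does not already settle precedence. If the forms or the tree show otherwise, the protocol text still needs to be aligned with them. The correction should be made, since it is cheap and bears on what the DSMB sees.

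**What to change.** 1. In Section 11.2 and Appendix C.3, limit the exemption to outcomes named in Sections 5.2, 5.3, 6.2 or Appendix E, and replace the open set of examples with that closed list.
2. Remove the lines for AST/ALT elevation, acute pancreatitis, the cytopenias and severe dermatologic reaction, so that serious cases follow the normal serious adverse event route. The alternative is to add the four to the daily collection in Section 6.2, which means extra data entry for every patient.
3. Reconcile Section 11.2, the opening of Appendix C and C.3 with Section 11.3 in one sentence that states which rule governs serious events graded unrelated. Say whether the relatedness wording in Appendix C applies only to the 24-hour notice.
4. Check that the C.4 decision tree and the case report forms agree with the revised text.

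The cost is wording in two or three places and possibly a few more adverse event forms among 30 patients. Removing the lines needs no new tests or staff. It will not capture non-serious events graded unrelated; that would need a separate decision about Section 11.2.

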## 11.3 Serious Adverse Events

Serious adverse event collection begins after randomization and study procedures have been initiated. If a patient experiences a serious adverse event after consent, but prior to randomization or starting study procedures, the event will NOT be collected. Study site personnel must alert the CCC of any **serious and study procedure related** adverse event within 24 hours of investigator awareness of the event. Alerts issued via telephone are to be immediately followed with official notification on the adverse event case report form. See Appendix C for reporting timelines for serious, unexpected, study related events (SAEs) and serious, unexpected suspected adverse reactions (SUSARs)

As per the FDA and NIH definitions, a serious adverse event is any adverse event that results in one of the following outcomes:

- Death
- A life-threatening experience (that is, immediate risk of dying)
- Prolonged inpatient hospitalization or re-hospitalization

As per <http://www.fda.gov/Safety/MedWatch/HowToReport/ucm053087.htm>: Report if admission to the hospital or prolongation of hospitalization was a result of the adverse event. Emergency room visits that do not result in admission to the hospital should be evaluated for one of the other serious outcomes (e.g., life-threatening; required intervention to prevent permanent impairment or damage; other serious medically important event).

- Persistent or significant disability/incapacity

As per <http://www.fda.gov/Safety/MedWatch/HowToReport/ucm053087.htm>: Report if the adverse event resulted in a substantial disruption of a person's ability to conduct normal life functions, i.e., the adverse event resulted in a significant, persistent or permanent change, impairment, damage or disruption in the patient's body function/structure, physical activities and/or quality of life.

Reportable serious adverse events that may not result in death, be life-threatening, or require hospitalization may be considered serious adverse events when, based upon appropriate medical judgment, they may jeopardize the patient and may require medical or surgical intervention to prevent one of the outcomes listed in this definition. Serious adverse events will be collected until hospital discharge, regardless of the investigator's opinion of causation.

## **12. DATA AND SAFETY MONITORING BOARD (DSMB)**

The principal role of the DSMB is to assure the safety of participants in the trial. They will regularly monitor data from this trial, review and assess the performance of its operations, and make recommendations to the steering committee with respect to:

- Review of adverse events
- Interim results of the study for evidence of efficacy or adverse events
- Possible early termination of the trial because of new external information, early attainment of study objectives, safety concerns, or inadequate performance
- Possible modifications in the clinical trial protocol
- Performance of individual centers

## APPENDICES

### Appendix A. Schedule of Events

Study Activity	Pre-enrollment	Day 1	Day 2	Day 3	Day 4	Day 5	Day 6	Day 7	Day 8 through Discharge	Day 29	Acute Care F/U (by phone if discharged prior to Day 7 or Day 29)	3 Mos. F/U
Eligibility assessment	X											
Pregnancy test (if applicable)	X											
Informed consent	X											
COVID Ordinal Outcome Score Assessment 	X		X	X	X	X	X	X	X	X	X	
Randomization		X										
Baseline Variable Data Collection		X										
Blood Sample Collection		X						X				
Nasal Swab Collection		X		X						X		
Sequential Organ Failure Assessment (SOFA)		X		X								
ARDS Evaluation 		X	X	X	X	X	X	X	X	X		
Study Drug Delivery		X										
Study Variable Data Collection 			X	X	X	X	X	X	X	X		
Assessment of Study Drug Adherence 		X	X	X	X	X	X					
Adverse Events Monitoring/Assessment		X	X	X	X	X	X	X		X	X	
Safety Outcomes Assessment		X	X	X	X	X	X	X	X	X		
Mortality Assessment								X		X	X	
Long-term Outcomes 												X

Assessed if patient remains hospitalized; assessed by telephone follow-up if participant has been discharged

Assessed in-person, by telephone or videophone.

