#### 2.1.2 Magnesium citrates as a Therapeutic for COVID-19

Recent recommendations, such as the cessation of remdesivir in intubated COVID-19 patients with severe pneumonia, illustrates an important clinical observation: much of COVID-19 mortality occurs after the virus has been cleared. Viral clearance typically occurs 9-20 days after symptom onset[3]. A similar monkey model of SARS-CoV infection in the African Green Monkey demonstrated clearance of virus from nasal turbinates, nasopharynx, tracheal, proximal and distal lungs within 5-10 days after infection[4]. Similarly, investigators reported that viral loads in SARS-CoV-2-challenged rhesus macaques remain elevated for 10-28 days following primary challenge[5].

A common clinical factor found in persons at risk for COVID-19 severity, such as aging, obesity, diabetes and hypertension, is gut dysbiosis and resulting low grade inflammation with loss of epithelial barrier function[6, 7]. A recent study noted that compared with healthy controls, COVID-19 patients had significantly reduced bacterial diversity, a significantly higher relative abundance of opportunistic pathogens, such as *Streptococcus*, *Rothia*, *Veillonella* and *Actinomyces*, and a lower relative abundance of beneficial symbionts[8, 9]. Another investigation

of faecal samples with signature of high SARS-CoV-2 infectivity had higher abundances of bacterial species, such as *Collinsella aerofaciens*, *Collinsella tanakaei*, *Streptococcus infantis*, *Morganella morganii*, and higher functional capacity for nucleotide de novo biosynthesis, amino acid biosynthesis and glycolysis, whereas faecal samples with signature of low-to-none SARS-CoV-2 infectivity had higher abundances of short-chain fatty acid producing bacteria, *Parabacteroides merdae*, *Bacteroides stercoris*, *Alistipes onderdonkii* and *Lachnospiraceae* bacterium in the stool of COVID-19 patients[10]. These observations support assessing for host metagenomic contributors to COVID-19 morbidity and mortality.

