#### **Exclusion Criteria**

- 1. Prisoner
- 2. Pregnancy
- 3. Breast feeding
- 4. Current infectious or noninfectious diarrheal illness
- 5. Unable to randomize within 21 days after onset of acute respiratory infection symptoms
- 6. Unable to randomize after hospital arrival
- 7. Colonic obstruction
- 8. Unresolved hypovolemia
- 9.  $\text{CrCl} < 30\text{ml/min}$
- 10. Hypermagnesemia
- 11. Diagnosis of Long QT syndrome
- 12. Known allergy to magnesium citrate or the probiotic Floranex
- 13. Unresolved electrolyte imbalance such as hypokalemia or hypocalcemia. The patient can be enrolled if electrolytes are corrected and sustained.
- 14. Receipt of  $> 1$  dose of magnesium citrate or any other colonic cleanser in the 7 days prior to enrollment
- 15. Inability to receive enteral medications
- 16. Refusal or inability to be contacted on Day 15 for clinical outcome assessment if discharged prior to Day 15
- 17. Concurrent medical illness that interferes with clinical assessmentPrevious enrollment in this trial
- 18. The treating clinical team does not believe equipoise exists regarding the use of magnesium citrate plus the probiotic Floranex for the treatment of this patient.
- 19. Participating in any other COVID-19 therapeutic trial

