### **Placebo Arm**

Participants randomized to the placebo arm will receive matching carbonated lemon water 296 mL PO once to be taken within a 4-hour period, (about 10 oz.) and 2 over-encapsulated microcrystalline pills capsules twice daily for six days or until discharge, whichever is earlier. The placebo will be flavored to match the taste of the interventional arm.

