### 5.2 Secondary Outcomes

1. Time to recovery, which is the time to the earlier of final liberation from supplemental oxygen or hospital discharge
2. Hospital mortality to 28-day mortality (assessed on Study Day 29 from randomization)
3. Time to discharge to 28 days after treatment
4. Quantitative change in nasal viral titer
5. Change in systemic CD4+ and CD8+ T cell cytokine expression
6. Change in Oxygen AUC of SaO2/FiO2 through Day 7
7. Quantitative change in systemic immune profile
8. Oxygen-free days through Day 28
9. Ventilator-free days through Day 28
10. Vasopressor-free days through Day 28
11. ICU-free days through Day 28
12. Hospital-free days through Day 28

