### **6.1 Baseline Assessments and Procedures: Hospital Presentation to Randomization (Day 1)**

- Inclusion/exclusion criteria screening
- Pregnancy test (if applicable)
- Informed consent
- Completion of COVID Ordinal Outcomes Scale
- Blood collection for CD4+ and CD8+ T cell cytokine expression
- Nasal Swab testing for SARS-CoV-2
- Completion of the Sequential Organ Failure Assessment (SOFA)
- Evaluation of Acute Respiratory Distress Syndrome (ARDS) by Berlin Criteria
- Baseline Variable Data Collection:
  - Hospital admissions data: date/time of presentation, origin (home, skilled nursing facility, rehabilitation/LTACH, nursing home, outside hospital, outside ICU), location at enrollment (ED, hospital ward, ICU)
  - Demographics (age, sex, race, ethnicity, height, weight)
  - Signs and symptoms/onset date including acute signs/symptoms such as altered mental status, acute hypoxemic respiratory failure, liver function tests, renal function, coagulation studies, SOC chest imaging results
  - Concomitant Medications/Medication History to include:
    - Chronic use of medications such as: corticosteroids, ACE inhibitors, angiotensin receptor blockers, non-steroids or anti-inflammatory drugs
    - Open label antivirals received such as remdesivir
    - Open label immunomodulators
    - Biologic therapy such a convalescent plasma
  - Comorbidities
  - Oxygen/ventilation assessment including S/F ratio, ventilation type, & vasopressor use (if applicable)
  - Vital signs, including highest respiratory rate, lowest systolic blood pressure, and highest heart rate in the 12 hours prior to enrollment (if available)
- Enrollment/Randomization
- First study drug administration

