#### **6.2.1.2 Day 3**

- Completion of SOFA assessment
- Nasal swab for SARS CoV-2 testing

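### Nasal swabs on Days 1, 3 and 29 leave the viral titer outcome without an informative measurement for the full regimen

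*Combined protocol and SAP*

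**What the plan says.** Section 5.2 lists "Quantitative change in nasal viral titer" as secondary outcome 4. It gives no time point, assay or analysis, and Section 7 does not mention the outcome.

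The Appendix A row "Nasal Swab Collection" is marked under Day 1, Day 3 and Day 29. Section 6 agrees on the first two: "Nasal Swab testing for SARS-CoV-2" is a baseline procedure (Section 6.1), and "Nasal swab for SARS CoV-2 testing" is the Day 3 item (Section 6.2.1.2). Section 6 lists no Day 29 swab, and Section 6.3.1 has discharged patients assessed at Day 29 by telephone. Blood, by contrast, is drawn on Day 1 and Day 7.

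On natural history, Section 2.1.2 states "Viral clearance typically occurs 9-20 days after symptom onset" and adds that viral loads in challenged macaques "remain elevated for 10-28 days following primary challenge".

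On entry, at least one respiratory symptom is required, together with laboratory confirmation in the 10 days before randomization. Exclusion item 5 reads "Unable to randomize within 21 days after onset of acute respiratory infection symptoms".

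On treatment (Section 4.2), the magnesium citrate bottle is taken once over 4 hours, with a second bottle possible. The capsules are taken "twice daily for six days or until discharge, whichever is earlier" in both arms.

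**The concern.** A change in titer can separate the arms only if it is measured while a fair share of patients still have virus to lose and after treatment has had time to act. Neither follow-up swab meets both conditions for the combined regimen. Day 29 lies beyond the clearance window that the protocol itself cites, and Day 3 comes partway through the probiotic course.

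If every titer at Day 29 equals the floor value L, the change is L minus the Day 1 titer. The between-arm difference in change is then the Day 1 difference with its sign reversed, which randomization makes zero on average whatever the treatment does. A null result on that contrast would say nothing about an antiviral effect, yet it could be read as evidence that there is none.

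**Working it through.** The documents give no effect size, standard deviation or power for titer, so there is no stated figure to reproduce. The check is calendar arithmetic.

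**Day count.** The protocol uses two conventions. Appendix A places randomization on Day 1, and 28-day mortality is assessed on Study Day 29, so Day n is n - 1 days after randomization. Section 4.1 says that Study Day 7 is 7 days after randomization, so Day n is n days after. Both are carried through.

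**Days since onset at each swab** = days from randomization + symptom days at entry (0 to 21).

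| Swab | Day n = n - 1 days after | Day n = n days after |
|---|---|---|
| Day 3 | 2 to 23 | 3 to 24 |
| Day 7 (not scheduled) | 6 to 27 | 7 to 28 |
| Day 29 | 28 to 49 | 29 to 50 |

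**Day 29 against the clearance window.** Even a patient randomized on the day of onset is 28 - 20 = 8 days (or 29 - 20 = 9) past the upper end. The macaque range runs from infection, not from symptoms. Adding the shortest incubation in Section 2.1.3 (2 days) puts Day 29 at least 28 + 2 = 30 days after infection, beyond the 28-day upper end of that range too.

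**If a few patients still shed at Day 29.** The true share is not in the documents, so a range is assumed. With 15 placebo patients, and power taken against complete elimination in the active arm (two-sided 5% level, normal approximation, rough at these counts):

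| Assumed positive on placebo | Expected positives of 15 | Power |
|---|---|---|
| 2% | 0.3 | about 8% |
| 5% | 0.75 | about 14% |
| 10% | 1.5 | about 23% |

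**Day 3 against the course.** Twice daily for six days is 12 dosing occasions. By the Day 3 swab about 4 to 6 are done: 4/12 = 33% to 6/12 = 50%. The initial magnesium citrate bottle is normally finished on Day 1.

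**What Day 7 would offer.** Assume, for illustration only, that clearance is uniform over days 9-20. The share still positive d days after onset is then (20 - d)/11 for d from 9 to 20.

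| Entry on symptom day | Day 3 | Day 7 | Day 29 |
|---|---|---|---|
| 7 | 11/11 = 100% or 10/11 = 91% | 7/11 = 64% or 6/11 = 55% | 0% |
| 10 | 8/11 = 73% or 7/11 = 64% | 4/11 = 36% or 3/11 = 27% | 0% |

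The two figures in a cell are the two day conventions.

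**Late entrants.** A positive test is needed within 10 days before randomization, but a positive Day 1 swab is not. In the same model, a patient entering on day 18 who tested positive on day t (9 or later) is still positive at entry with probability 2/(20 - t): 2/11 = 18% for t = 9, 2/5 = 40% for t = 15, and 2/3 = 67% for t = 17. Some late entrants may therefore have no detectable virus to lose. How many depends on entry and test dates, which the documents do not give.

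**The case against.** The best defence is that Day 3 fits the stated rationale. The cleansing dose is normally complete on Day 1, and Section 2.1.2 reports improvement within 24-72 hours of cleansing in three patients and doubts that probiotics can alter the gut microbiome quickly. Day 3 is 48-72 hours after randomization, and most early entrants should still have virus then. The capsules also stop at discharge, so six days is a maximum. This stands: Day 3 is a usable early measurement. It does not supply one for the combined regimen that the trial is set up to test.

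A reader might infer that every patient will be negative by Day 29, or that the swab is worthless in principle. The documents do not go that far. Section 2.1.2 describes typical clearance, not an upper bound, and a few patients may shed for longer. The sensitivity table shows that with 15 per arm this would add very little.

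A reader might also infer that outcome 4 cannot show any effect on titer, or that only 18% of patients entering on day 18 would be positive at baseline. The first ignores Day 3. The second is the worst case, because it ignores a more recent qualifying positive test.

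It is fair to add that the protocol never says the outcome is change to Day 29. But whichever of the scheduled swabs is used, none falls between Day 3 and Day 29.

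**Conclusion.** The concern holds for the full regimen. Day 29 is 28-50 days after onset across both day conventions and is expected to be at the floor in essentially all patients in both arms. Day 3 reflects the initial magnesium citrate dose plus about 33-50% of a full probiotic course. Outcome 4 therefore has no informative titer after the course.

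The Day 29 conclusion rests on the protocol's own clearance window and needs no assumption about the shape of clearance within it. The Day 7 shares of 55-64% and 27-36% do rest on the uniform assumption and on the chosen entry days. They also describe positivity, whereas the endpoint is quantitative, so they are illustrative.

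This is one of twelve secondary outcomes in a 30-patient trial. The primary analysis is not affected. Severity is minor to moderate.

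**What to change.** **Schedule.** In Appendix A, move the Day 29 swab to a fixed Day 7 for all patients and add it to Section 6. Take it with the Day 7 blood draw if the patient is still in hospital, and otherwise by whatever out-of-hospital route the Day 29 swab would have needed. Do not time it by discharge: time to discharge is itself an outcome, so if treatment speeded discharge, treated patients would be swabbed earlier, when titers are higher. Record the actual swab date, and state which day count applies.

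**Definition.** Define outcome 4 as titer at Day 3 and Day 7, adjusted for Day 1 titer and for symptom duration before randomization, among patients detectable on the Day 1 swab. Detectability on Day 1 is a baseline characteristic, so the restriction keeps the randomized comparison. Report by arm the number undetectable at baseline and the number of missing Day 7 swabs.

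**Cost.** The number of swabs is unchanged; only Appendix A, Section 6 and the outcome wording change. Late confirmation of clearance is lost, and some discharged patients will miss the Day 7 swab. Day 7 is itself partly limited by the floor in patients who enter later, which is why Day 3 should be kept.
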